#### 12.1.1.2 MS Relapse

MS relapse definition: appearance of a new neurological abnormality or worsening of previously stable or improving pre-existing neurological abnormality, separated by at least 30 days from onset of a preceding clinical relapse-qualifying event [5]. The abnormality must have been present for at least 24 hours and occurred in the absence of fever ( $< 37.5^{\circ}\text{C}$ ) or known infection.

Severe relapses involve 1) at least one of the following functional systems: motor, cerebellar, brainstem, spinal cord and 2) lead to an increase in EDSS of at least 1 point. A patient may report symptoms indicative of a relapse at a scheduled visit or at any other time.

Patients will be instructed to contact the Investigator if he/she develops new or reoccurring or worsening neurological signs/symptoms indicative of relapse. At each scheduled visit, the patient will also be asked whether such symptoms have occurred. If a patient reports new neurological symptoms or worsening of previous symptoms, a relapse assessment will be performed and sent for confirmation to the Medical Monitor.

Reporting of relapse: MS relapses should not be recorded as adverse events. However, MS relapses will be recorded on a separate relapse form in the eCRF. In addition, all relapses reported by the Investigators in the eCRF will be reviewed individually on an ongoing basis by an expert neurologist to decide whether the event qualifies for a true relapse in the context of this study (see definition above).

Occasional isolated symptoms that according to the Investigator are caused by MS, but do not constitute a full MS relapse, should be reported as an adverse event.

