- if at least 3 patients experience AEs graded as 'moderate' and at least possibly related to the IMP within the same dose level of CLS12311/placebo
- If at least 3 patients (irrespective of the dose group) show an increase of >5 new lesions (CEL or new/enlarging T2) at [REDACTED] compared to the average number of new brain lesions (as defined above) observed during baseline
- if a confirmed relapse (irrespective of the dose group), assessed as severe, occurred within 4 weeks after the last dosing

The DSMB shall give recommendations on the following main outcomes:

- stop further treatment or lower further dosing in individual patients
- stop recruitment and/or treatment or lower dose for a specific treatment arm
- stop recruitment and/or treatment for the clinical trial
- continue the clinical trial as per protocol
- any other trial modification (e.g. additional visits, assessments)

Any recommendation will be explicitly documented in the meeting minutes.

Based on the DSMB recommendations, the Study Steering Committee will decide on actions to be taken as outlined above.

For the DSMB meetings, the DSMB will receive patient listings and statistical summaries, consisting of at least the following in addition to all available data on the patient(s) that made the meeting necessary:

- All patients who experienced SAEs (including relationship and severity)
- All patients who experienced AEs (including relationship and severity)
- All patients who experienced AEs within one day following infusion of CLS12311/placebo including severity and relationship
- All patients who experienced a relapse
- Number of new brain lesions (CEL and new/enlarging T2)
- EDSS scores
- Safety relevant protocol deviations

Detailed requirements on the presentation of listings and summaries and details of the premise and the scope of the DSMB will be specified in the DSMB Charter.

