#### 5.1.2 Autoimmune Pathogenesis of MS and Role of T cells

The pathogenesis of MS is driven by a complex interaction of genetic and environmental factors. Major environmental risk factors include sun exposure, vitamin D deficiency, smoking, obesity, Epstein Barr virus (EBV) infection and particularly infectious mononucleosis during early adulthood. The most important genetic risk factor in MS is the human leukocyte antigen (HLA) DR15 haplotype. Most of the other >200 genetic variants that confer a risk of developing the disease are associated with immune pathway genes [6]. Data from both human and animal studies suggest that the adaptive immune system and in particular autoreactive CD4+ T cells and B cells are important effector cells in the autoimmune pathogenesis of MS [7]. The fact that most of the genetic susceptibility for MS is conferred by the DR15 haplotype, supports the role of CD4+ T cells, since CD4+ T cells recognize antigens in the context of HLA-class II molecules [8]. Further evidence for the importance of autoreactive CD4+ T cells, comes from studies in blood and CSF of MS patients. The frequency of activated CD4+ T cells reactive to main constituents of the myelin sheath, such as myelin basic protein (MBP), proteolipid protein (PLP) and myelin oligodendrocyte glycoprotein (MOG), is increased in the peripheral blood of MS patients [9] [10] [11]. In particular, T cells targeting a set of immunodominant peptides from MBP, MOG and PLP (MBP13-32, MBP111-129, MBP146-170, PLP139-154, MOG1-20 and MOG35-55) with high avidity and a Th1 or Th1\* (secreting IFN- $\gamma$  and IL-17) cytokine phenotype, can be found in a large

fraction of RRMS patients [12]. Further evidence for the importance of myelin-reactive T cells comes from a clinical trial in MS, where an experimental therapy induced MBP 83-99-reactive Th1 CD4+ T cells, which caused exacerbation of disease [13].

More recent studies focusing on T cells, which are clonally expanded in brain lesions of MS patients, identified further non-myelin proteins as target antigens of the autoimmune response in MS patients [14; 15].

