#### 13.1.1 Adverse Events

An Adverse Event (AE) is any untoward medical occurrence in a patient or clinical investigation subject administered a pharmaceutical product and which does not necessarily have a causal relationship with this treatment. An AE can therefore be any unfavourable and unintended sign (including an abnormal laboratory finding), symptom, or disease temporally associated with the use of an investigational medicinal product (IMP), whether or not related to the IMP or study treatment/procedures.

The findings from physical examinations will be compared with those at baseline (screening visit 1) and all new findings and deterioration of baseline findings will be documented as AEs.

Vital sign, laboratory or ECG abnormalities should not be documented as AEs unless they are accompanied by clinical symptoms, require treatment, fulfil any SAE criterion, cause a change in the study schedule or are considered clinically significant in the Investigator's judgment.

In case the vital sign / laboratory / ECG abnormalities are a sign of a medical condition, the condition should be documented as an AE and not the abnormal sign (e.g. elevated blood pressure → primary hypertension; blood glucose increased → type 2 diabetes mellitus).

MS Relapse and new MS lesions are not considered AEs (see 12.1.1.2).

AE collection will occur from the start of study through the end of the follow-up period.

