Risk of a transfusion reaction will be mitigated by thorough tracking of the autologous blood product.

**Immune activation and disease exacerbation:** The aim of the therapy is the downregulation of an autoreactive immune response through the induction of immune tolerance. However, the induction of an immune response leading to exacerbation of disease cannot be fully excluded. The type of trial, which is based on using MRI measures of inflammation as a sensitive safety measure, is considered optimal in this regard, and clear rules triggering safety data review by a DSMB (see section 19.1.3) have been defined to minimize risks and enable medical actions at the earliest possible time point.

**Risk of infection:** Some biologic and non-biologic therapies for the treatment of MS have been associated with an increased risk of infection. As a measure of precaution, the Investigator or study physicians are required to carefully monitor for any signs or symptoms of infection (see section 14.5).

**Carcinogenicity:** Peptide-coupled RBCs are mature autologous cell populations and do not have a cell nucleus and thus do not have the ability to proliferate. It has not been described that MS patients have increased risks to develop tumors [58].

[REDACTED]

**Reproductive and developmental toxicity:** Reproductive and developmental toxicity was not assessed in pre-clinical studies. Available data do not suggest any reproductive or developmental toxicity or influence on reproductive performance to arise from the single injection of autologous

cells. Nevertheless, the patients will be informed about the remote potential of such risks and will have to sign an informed consent that they have to use acceptable methods of contraception.

**Injection site reactions:** Peptide-coupled RBCs will be administered by IV infusion. The medication will be released slowly as a drip from a bag and into a tube that is attached to the needle. It is common for a patient to experience reactions at the injection site as a side effect of the venous puncture. Common skin reactions include redness, bruising, pain, or swelling. These symptoms usually resolve on their own within a short period. Slowing of the infusion rate may be necessary in the event of an infusion reaction.

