#### 14.5 Special Warnings and Precautionary Measures

**Allergic/anaphylactic and other infusion-related reactions:** As a precautionary measure, patients must be kept under medical supervision for at least 2 hours following IMP/placebo administration during the first treatment cycle to allow for an adequate observation and adequate treatment in case of potential allergic or other infusion related reactions. During the second treatment cycle the observation period is 1h following IMP administration. Furthermore, during the first treatment cycle, a telephone-based assessment of AEs will be done the day after IMP/placebo administration. In case of severe allergic (anaphylactic) reactions, standardized medical treatment should be applied. An example for an emergency treatment is given in the Appendix 24.2.

**Infection:** Some biologic and non-biologic therapies for the treatment of MS have been associated with an increased risk of infection. As a measure of precaution, the Investigator or Study Physicians are required to carefully monitor for any signs or symptoms of infection such as, but not limited to, increased body temperature, malaise, sweats, cough, dyspnea etc.

A **Data and Safety Monitoring Board (DSMB)** has been established to assess safety of patients treated in the study (for details on DSMB responsibilities see section 19.1.3).

**Investigators** are instructed not to proceed with the next IMP infusion if:

- the study participant is pregnant
- the study participant experienced allergic reaction in prior IMP administration
- the study participant experienced a severe infusion-related reaction in prior IMP administration
- the study participant experienced a serious AR to prior IMP administration
- the study participant experiences an SAE at the time of IMP infusion or any other serious medical condition, which poses a threat to the safety of IMP administration
- the Sponsor or Steering Committee or DSMB have decided to not continue IMP administration in the trial arm concerned

In case of questions or uncertainties regarding IMP administration following adverse events, the Investigator should contact the medical monitor (primary contact) or the Sponsor's Medical Representative. Contact details are given at the beginning of the study protocol.

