 - AEs for which “Other action taken” is documented as “No further blood donations” or “Patient withdrawn from the trial”
- **TEAEs leading to death:** AEs documented as having a “fatal” outcome.

The intensity or severity of an adverse event is defined according to the Common Terminology Criteria for Adverse Events (CTCAE, version 5.0, 2017) and provided in Table 3.

Table 3 Adverse Event Intensity Classification

Intensity	Explanation
Mild (Grade 1)	
 • Asymptomatic or mild symptoms • Clinical or diagnostic observations only • Intervention not indicated
Moderate (Grade 2)	
 • Moderate, minimal, local or non-invasive intervention indicated limiting age-appropriate instrumental activities of daily living (ADL)
Severe (Grade 3)	
 • Severe or medically significant but not immediately life-threatening; hospitalization or prolongation of hospitalization indicated; disabling symptoms limiting self-care activities of daily living
Life-threatening (Grade 4)	
 • Life-threatening consequences: urgent intervention indicated
Death (Grade 5)	
 • Death related to AE or to multiple sclerosis

AEs of special interest are defined as severe AEs (Grade of ≥ 3) which are related to the IMP and occurring within one day following infusion of CLS12311/placebo: dyspnea, tachycardia, fever, chills, malaise, shock, infection, allergic reaction, renal or liver failure. Adverse events of special interest will be assessed by the investigator.

TEAEs will be summarized using crude and exposure-adjusted incidence rates. A crude incidence rate will be calculated as number of patients with a TEAE divided by number of patients at risk (at the beginning of the study). An exposure-adjusted TEAE incidence rate per 1 patient-year will be defined as number of patients who experienced a TEAE divided by the total time from the blood donation until occurrence of the event for those who experienced an event, or the end of the safety follow-up for those who did not, multiplied by 365.25, among patients at risk at the beginning of the study:

$$I_{AE} = \frac{n}{\sum_i t_i} \times 365.25 = \frac{n}{T} \times 365.25$$

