5.5.2 Multiple Sclerosis Relapse

MS relapse is defined as an appearance of a new neurological abnormality or worsening of previously stable or improving pre-existing neurological abnormality, separated by at least 30 days from onset of a preceding clinical relapse-qualifying event. The abnormality must be present for at least 24 hours and occurred in the absence of fever (< 37.5°C) or known infection.

Severe relapses involve 1) at least one of the following functional systems: motor, cerebellar, brainstem, spinal cord and 2) lead to an increase in EDSS of at least 1 point.

MS relapse assessment will be documented in the eCRF. The following parameters will be collected:

- MS relapse status (resolved/ ongoing)
- Start date
- New neurological abnormality or worsening of previously stable or improving pre-existing neurological abnormality, separated by at least 30 days from onset of a preceding clinical relapse-qualifying event (yes – new/worsening, no)
- Did the symptoms last for at least 24 hours (yes/no)
- Did the symptoms occur in absence of fever or known infection (yes/no)
- Hospitalization status and the reason of hospitalization (patient disability status, routine process for high dose corticosteroid treatment, other therapies as consequence of relapse)
- Plasmapheresis for their MS relapse (yes/no)
- End of symptoms (date (or ongoing), outcome (death, no recovery, complete recovery, partial recovery))
- Short description
- Confirmed relapse by neurological experts (yes/no)
- Meeting criteria for severity as assessed by neurological experts (yes/no)

The following MS relapse parameters will be summarized:

- Patients experiencing an MS relapse according to the investigator
- Patients with centrally confirmed MS relapses
- Patients with severe centrally confirmed MS relapse
- Annualized Relapse Rate (ARR), defined as total number confirmed MS relapses divided by the number of subject-years of post-treatment study participation duration (including the treatment phase and safety follow-up phase):

$$ARR = \frac{\text{number of relapses}}{\text{post – treatment study participation duration (days)}} \times 365.25$$

The following statistical output will be presented:

Table 15.2.2 Summary of MS Relapse – Modified Safety Analysis Set

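### A serious MS relapse suspected to be caused by CLS12311 has no stated route to an SAE or SUSAR report, because all qualifying relapses are excluded from AE recording and the relapse form lists no relationship or seriousness item

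*Protocol*

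**What the plan says.** Protocol 12.1.1.2 states that "MS relapses should not be recorded as adverse events"; they go on a separate eCRF form and an expert neurologist reviews each one. Section 13.1.1 agrees: "MS Relapse and new MS lesions are not considered AEs". Neither section excepts a relapse that meets a seriousness criterion. Section 12.1.1.2 does, however, make isolated MS symptoms that fall short of a full relapse reportable as AEs.

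Worsening of disease by relapse is part of the primary safety endpoint (protocol 6 and 12.1.1; SAP 2.2.1). Protocol 13.4.5 accepts that "the induction of an immune response leading to exacerbation of disease cannot be fully excluded".

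The relapse fields in SAP 5.5.2 include "Hospitalization status and the reason of hospitalization (patient disability status, routine process for high dose corticosteroid treatment, other therapies as consequence of relapse"), an outcome list that contains death, central confirmation, and an expert yes/no on severity. They include no relationship to treatment and no seriousness. The AE fields in SAP 5.5.1 include both.

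The synopsis (Data and Safety Monitoring) requires an extra DSMB meeting "if a confirmed relapse (irrespective of the dose group), assessed as severe, occurred within 4 weeks after the last dosing". Other triggers are AE-based, among them one patient with a severe AE at least possibly related to the IMP, and one is MRI-based.

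**The concern.** Keeping relapses out of the AE system is natural when relapse is an efficacy outcome. Version 7.0 has no efficacy objective, and relapse is now a safety endpoint. The exclusion has stayed in full, so the one judgement that separates natural disease from product harm, relationship to CLS12311, is not collected for the event in which that harm would show.

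This touches dosing decisions as well as tables. Under protocol 7.1 (Safety Monitoring and DSMB Review), the sponsor's review before second dosing of patients 2, 4 and 5 includes serious and severe events attributed to peptide-coupled RBCs. No such attribution would exist for a relapse.

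In the report, a hospitalised or fatal relapse, not being an AE, would be absent from the serious, related and leading-to-death TEAE tables. SAP 5.5.2 does not summarise hospitalisation or fatal outcome of relapses either; these would appear only in the relapse listing and, for a death, in the disposition output.

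**Working it through.** The plan states no figure to reproduce. The check is mainly a trace through the definitions.

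**Step 1, the chain.**
- AE: relapse excluded (protocol 12.1.1.2, 13.1.1).
- Adverse reaction: an AE with a suspected causal relationship (13.1.6).
- SUSAR: a suspected adverse reaction that is serious and unexpected (13.1.8).
- 24-hour report: SAEs (13.2.2).
- DSMB trigger for a severe related event: an AE (synopsis).
- Bar to the next infusion in 14.5, first relevant item: "the study participant experienced a serious AR to prior IMP administration". This needs an adverse reaction, hence an AE.

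A qualifying relapse drops out at the first link, so no later link is open to it. For the SAE link this is an inference: 13.1.2 names no relapse exclusion, but 13.1.1 takes relapses out of the class from which SAEs are recorded.

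**Step 2, the same disease process at two intensities.**

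| Item | MS symptom short of a relapse | Full relapse |
|---|---|---|
| Form | AE page | Relapse form |
| Relationship to treatment | Rated | Not in field list |
| Seriousness | Rated | Not in field list |
| Missing causality treated as related (13.1.4) | Yes | Does not apply |
| 24-hour report if serious | Yes | No stated route |
| DSMB trigger, severe related AE | Can meet it | Cannot meet it |
| DSMB trigger, severe relapse | Cannot meet it | Can meet it, within 4 weeks |

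The milder event receives the fuller safety assessment.

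**Step 3, reach of the relapse-specific trigger.** Inputs: follow-up of at least 48 weeks (protocol 7); CLS12311 given within 13 weeks of enrolment (10.2.4); a 4-week window (synopsis).
- Window closes: 13 + 4 = week 17.
- Weeks after that: 48 − 17 = 31; 31/48 = 65%. This equals the 31-week safety follow-up.
- Share covered if only the final dose counts: 4/48 = 8.3%.
- Upper bound if each of up to four dosing days opens its own window and none overlap: 16/48 = 33%.

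These are nominal; dosing intervals are redacted and visits may be postponed.

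**Step 4, passages that do not agree.**
- SAP Table 3 defines Grade 5 as "Death related to AE or to multiple sclerosis"; protocol Table 13-1 confines Grade 5 to death related to an AE.
- The note on death in 13.1.2 says the condition that led to death is to be reported and gives underlying disease as an example. That would bring in a fatal relapse, which 13.1.1 excludes.
- Section 13.1.1 makes all new or worsened physical examination findings AEs, then excludes relapses, which commonly present as such findings.
- Section 13.4.5 refers to 19.1.3 for the DSMB trigger rules. Section 19.1.3 lists none; they stand only in the synopsis.

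**The case against.** Relapses are far from unwatched. Escalation depends on (S)AEs and relapses together, with data entry within 24 hours (7.1). Every relapse has expert review, the DSMB receives all patients with a relapse, and one early severe confirmed relapse forces a DSMB meeting with no causality judgement, which asks less than the AE trigger does. The relapse table and Listing 16.2.4 would show any relapse among nine patients. Late relapses are also hard to attribute, because another DMT may be started in follow-up (7.2). All of this stands and limits the harm. None of it supplies a causality rating or a serious-event report.

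A reader might infer more than the documents support:

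- *That such a relapse can never become an SAE, and that authorities would hear nothing.* Section 13.1.2 opens with any untoward occurrence, and its note on death points towards a fatal relapse. Section 13.2.2 also provides for notifying other significant safety issues. What is missing is a stated route, site obligation and clock.
- *That 14.5 would let dosing continue after a disabling relapse.* It has a residual item for any other serious medical condition that threatens safe administration, and an item for a sponsor, Steering Committee or DSMB decision.
- *That exacerbation is the main named risk and has occurred with this product class.* Section 13.4.5 lists it among several risks and calls aggregates a major concern. Section 5.1.2 cites a trial in which "an experimental therapy induced MBP 83-99-reactive Th1 CD4+ T cells, which caused exacerbation of disease", but the reference is to an altered peptide ligand. For peptide-coupled cells, 13.4.5 reports no sign of toxicity in nineteen patients.
- *That several serious events would be lost.* Nine patients give 9 × 48/52 = 8.31 patient-years. At assumed annual relapse rates of 0.3 to 0.7 that is 2.5 to 5.8 relapses, but these are all relapses. The gap concerns only those that are serious and suspected to be related, or fatal, and the documents give no basis for estimating that number.

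The actual eCRF, the DSMB Charter and the reference safety information are not part of the documents and may narrow the gap.

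**Conclusion.** The point holds as a gap in reporting and attribution. A site that follows the plan exactly would give a serious, product-suspected relapse no relationship rating, no formal seriousness rating and no stated 24-hour SAE or SUSAR route. The relapse-specific DSMB trigger only partly compensates: it needs confirmation, a severe rating and timing within 4 weeks after the last dosing, and nominally leaves 31 of 48 weeks (65%) uncovered.

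This is a cheap, specific safety improvement. It does not show that relapses go unmonitored or would be hidden in the results. It rests on SAP 5.5.2 being a full account of the relapse form, on the AE exclusion carrying through to SAEs, and on the nominal dosing schedule.

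**What to change.** 1. Add two investigator-rated items to the relapse form and to SAP 5.5.2: relationship to CLS12311/placebo, and seriousness by the 13.1.2 criteria.
2. In protocol 12.1.1.2 and 13.1.1, state that a relapse that meets an SAE criterion and is judged related, or that is fatal, is also reported under 13.2.2 and assessed for expectedness. All other relapses stay on the separate form only.
3. Show these events in the TESAE and related-TEAE tables, with a footnote that they are already in the relapse count, so that they are not read as additional events.
4. Reconcile the exclusion in 12.1.1.2 and 13.1.1 with 13.1.2, and SAP Table 3 with protocol Table 13-1, for deaths due to MS.

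SAP Final 2.0 was issued after the data review. If collection has ended, have investigators rate the recorded relapses retrospectively and document this in the SAP, or in an addendum if the database is locked, labelled as retrospective.

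Cost: two fields, a short paragraph in the protocol and some SAP wording. The downside is a few more SAE reports, some of which will reflect natural disease. With nine patients that burden is small.
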